**Table 8-1. Definition of Responses Categories**

| Category                | Definition  |
|-------------------------|---|
| Complete Remission (CR) | 
 
Documented “complete remission” or “complete response” or “No evidence of disease” in the EHR and
 
All peripheral blooda (within a 2-week period before or after the date of BM biopsy) and BM indices meeting the threshold for CR as defined in the IWG 2006 MDS response criteria and
 
All peripheral blood resultsa and the corresponding BM biopsy completed within a 4-week period before or after the CR documentation date
 
Cases that have the required peripheral blood and BM indices meeting the threshold for CR as defined in the IWG 2006 MDS response criteria but lack EHR documentation of CR will be adjudicated by an independent assessor
 
  |
| Real-world CR (rw-CR)   | 
 
EHR documentation of CR (as above) with or without all corresponding IWG 2006 indices; partial availability of indices will also fall into this category
 
  |
| Partial Remission (PR)  | 
 
Documented “partial remission” or “partial response” or “improved disease” or “responding disease” or similar termsb in the EHR and
 
All peripheral blooda (within a 2-week period before or after the date of BM biopsy) and BM indices meeting the threshold for PR as defined in the IWG 2006 MDS response criteria and
 
All peripheral blood resultsa and the corresponding BM biopsy completed within a 4-week period before or after the PR documentation date
 
Cases that have the required peripheral blood and BM indices meeting the threshold for PR as defined in the IWG 2006 MDS response criteria but lack EHR documentation of PR will be adjudicated by an independent assessor
 
 |

| Category   | Definition  |
|--|---|
| Real-world PR (rw-PR)  | 
 
EHR documentation of PR (as above) with or without all corresponding IWG 2006 indices; partial availability of indices will also fall into this category
 
  |
| Marrow CR (mCR)  | 
 
Based on BM blast count, without requirement of EHR documentation
 
BM: <math>\leq 5\%</math> myeloblasts and decrease by <math>\geq 50\%</math> over pretreatment count
 
   |
| Hematologic Improvement (HI)   | 
 
HI indices as defined in the IWG 2006 criteria, without requirement of EHR documentation
 
  |
| Relapse After CR or PR   | 
At least 1 of the following:
 
 
Return to pretreatment BM blast percentage
 
Decrement of <math>\geq 50\%</math> from maximum remission/response levels in granulocytes or platelets
 
Reduction in Hb concentration by <math>\geq 1.5</math> g/dL
 
Transfusion dependence
 
  |
| Stable disease (SD) or Real-World Stable Disease (rw-SD) or Indeterminate Response | 
 
EHR documentation of disease as “stable” and
 
IWG 2006 indices not meeting the threshold for PD (see below) for a minimum of 8 weeks
 
   |
| Progressive Disease (PD)   | 
 
EHR documentation of “progressed disease” or “worsening of disease” or similar terms or
 
 
For patients with:
 
 
Less than 5% blasts: <math>\geq 50\%</math> increase in blasts to <math>> 5\%</math> blasts
 
5%-10% blasts: <math>\geq 50\%</math> increase in blasts to <math>> 10\%</math> blasts
 
10%-20% blasts: <math>\geq 50\%</math> increase in blasts to <math>> 20\%</math> blasts
 
20%-30% blasts: <math>\geq 50\%</math> increase in blasts to <math>> 30\%</math> blasts
 
 
Any of the following:
 
 
At least 50% decrement from maximum remission/response in granulocytes or platelets
 
Reduction in Hb by <math>\geq 2</math> g/dL
 
Transfusion dependence
 
 |

BM bone marrow; CR complete remission; EHR electronic health record; Hb hemoglobin; HI hematologic improvement; IWG International Working Group; mCR marrow complete remission; MDS myelodysplastic syndrome; PD progressive disease; PR partial remission; rw CR real world CR; rw PR real world partial remission; rw SD real world stable disease  
 Cytogenetic responses are not defined for simplicity.

All responses meeting the CR, rw CR, PR, and rw PR will be subject to adjudication by an independent assessor who will be a board certified hematologist.

- If the peripheral blasts are available, they would be used in the response adjudication. If not available, they will be considered as absent (0%). The results of Hb, platelets and absolute neutrophil count for meeting the threshold for IWG 2006 MDS response criteria should have been obtained from the same sample (within the 4 week window of response documentation date).
- In order to align with McKesson’s standard reviewer training of response documentation and to reduce confusion, ‘improved disease’ or ‘responding disease’ will be documented as “Response Not Otherwise Specified (NOS)” in eCRF. During analysis this can be combined with/re categorized into “partial remission” group.

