## 7. RESEARCH QUESTIONS AND OBJECTIVES

The primary objective of this study is as follows:

- To evaluate the effectiveness of AZA monotherapy as assessed by CR rate defined by the International Working Group (IWG) 2006 MDS criteria in patients with intermediate-, high-, and very high-risk MDS

The secondary objectives of this study are as follows:

- To evaluate additional measures of effectiveness including the real-world CR (rw-CR) rate, objective response rate (ORR) defined by IWG 2006 MDS criteria, real-world objective response rate (rw-ORR), duration of complete remission (DCR) and its real-world - equivalent, and the duration of response (DOR) and its real-world equivalent of AZA in this study population
- To evaluate progression-free survival (PFS), time to next treatment (TTNT), and overall survival (OS) of AZA in this study population

The exploratory objectives of this study are to evaluate the following in this study population:

- [REDACTED]
- [REDACTED]
- [REDACTED]
- [REDACTED]

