#### 8.1.1. Primary Endpoint

**Complete Remission Rate** is defined as the proportion of patients who achieve a CR as documented within their EHRs, with confirmation of corresponding BM and peripheral blood parameters as defined per IWG 2006 MDS response criteria {Cheson 2006}, during the treatment period with AZA or prior to the initiation of next MDS treatment.

Definitions of responses categories are shown in [Table 8-1](#) below.

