**Appendix 2. International Working Group 2006 criteria {Cheson 2006}**

**Table 13-1. 2006 International Working Group Response Criteria for Altering Natural History of MDS**

| Category                  | Response Criteria (Responses Must Last at Least 4 Weeks)  |
|---------------------------|---|
| Complete Remission        | BM: $\leq 5\%$ myeloblasts with normal maturation of all cell lines
Persistent dysplasia will be noted
Peripheral blood 
 
Hb <math>\geq 11</math> g/dL
 
Platelets <math>\geq 100 \times 10^9/L</math>
 
Neutrophils <math>\geq 1.0 \times 10^9/L</math>
 
Blasts 0%
 
   |
| Partial Remission         | All CR criteria if abnormal before treatment except:
BM blasts decreased by $\geq 50\%$ over pretreatment but still $> 5\%$
Cellularity and morphology not relevant   |
| Marrow CR                 | BM: $\leq 5\%$ myeloblasts and decrease by $\geq 50\%$ over pretreatment
Peripheral blood: if HI responses, they will be noted in addition to marrow CR  |
| Hematological Improvement | Please refer to Table 13-2 below  |
| Stable Disease            | Failure to achieve at least PR, but no evidence of progression for $> 8$ weeks  |
| Failure                   | Death during treatment or disease progression characterized by worsening of cytopenias, increase in percentage of BM blasts, or progression to a more advanced MDS FAB subtype than pretreatment  |
| Relapse After CR or PR    | At least 1 of the following: 
 
Return to pretreatment BM blast percentage
 
Decrement of <math>\geq 50\%</math> from maximum remission/response levels in granulocytes or platelets
 
Reduction in Hb concentration by <math>\geq 1.5</math> g/dL or transfusion dependence
 
   |
| Cytogenetic Response      | Complete 
 
Disappearance of the chromosomal abnormality without appearance of new ones
 
 Partial 
 
At least 50% reduction of the chromosomal abnormality
 
  |

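### Table 8-1 sets no minimum duration for CR, PR or marrow CR, while Appendix 2 puts a 4-week minimum on the same IWG 2006 responses; the passages must be reconciled

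*Protocol*

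**What the plan says.** Section 7 of the protocol makes the primary objective the effectiveness of azacitidine "as assessed by CR rate defined by the International Working Group (IWG) 2006 MDS criteria". Section 8.1.1 defines the endpoint as a CR documented in the record "with confirmation of corresponding BM and peripheral blood parameters as defined per IWG 2006 MDS response criteria".

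Table 8-1 turns this into rules:

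- **CR:** a remission note; blood and "BM indices meeting the threshold for CR as defined in the IWG 2006 MDS response criteria", with the blood results within 2 weeks of the marrow; and "the corresponding BM biopsy completed within a 4-week period before or after the CR documentation date". A footnote adds that Hb, platelets and neutrophils "should have been obtained from the same sample (within the 4 week window of response documentation date".
- **PR:** the same structure with the PR threshold.
- **Marrow CR (mCR):** "Based on BM blast count, without requirement of EHR documentation", followed by the blast rule.
- **Stable disease:** includes a minimum of 8 weeks.

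Appendix 2, Table 13-1 reproduces the IWG 2006 criteria. Its column heading, which covers CR, PR and marrow CR, reads "Response Criteria (Responses Must Last at Least 4 Weeks".

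**The concern.** The objective points to a set of criteria that includes a minimum duration. The operational table takes over only the thresholds. Its 2-week and 4-week figures say how close in time the blood, marrow and note must be to one another. They do not say how long the response must hold.

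The gap could reach the data. Section 8.8 plans algorithms that derive outcomes so that they need not be interpreted by hand, and an algorithm applies only what is written. Section 8.9 sends to the adjudicator the responses that satisfy the protocol's definitions, which are those of Table 8-1. Short-lived responses could then enter the numerator of the primary endpoint.

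Sections 6.1 and 8.7.4 say the results will be compared with the single-arm Study 5F9005 to judge what magrolimab adds. If one side applies the 4 weeks and the other does not, part of any difference in CR is a difference of definition.

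**Working it through.** **Step 1. The two tables side by side.**

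| Response | Table 8-1: duration | Table 8-1: link to IWG 2006 | Appendix 2, Table 13-1: duration |
|---|---|---|---|
| CR | none stated | threshold only | at least 4 weeks |
| PR | none stated | threshold only | at least 4 weeks |
| Marrow CR | none stated | none; blast rule restated | at least 4 weeks |
| Stable disease | 8 weeks | PD threshold not met | more than 8 weeks |

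The stable disease row shows that Table 8-1 states a duration where its authors meant to.

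**Step 2. Two test patients**, each with a remission note, a qualifying marrow and no earlier qualifying counts.

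- *Patient A:* Hb 11.2 g/dL at the qualifying sample, 9.6 g/dL one week later. The fall is 11.2 − 9.6 = 1.6 g/dL, which meets the relapse rule of Table 8-1 (at least 1.5 g/dL). This is a CR under the CR row, but it ended within 4 weeks and so fails Appendix 2.
- *Patient B:* Hb 11.2 g/dL, then 10.8 g/dL. The fall is 0.4 g/dL, so there is no relapse, yet the value is now below the CR threshold of 11 g/dL. The documents do not say whether the response has ended.

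Patient A shows that the two definitions can classify the same chart differently. Patient B shows that adding the words 4 weeks would not be enough, because what ends a response must also be stated.

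**Step 3. Direction and reach.** Every response that satisfies the thresholds and lasts 4 weeks also satisfies the thresholds alone. Dropping the duration can therefore only raise the count or leave it unchanged. For CR this reaches the primary rate. For CR, PR and marrow CR it reaches ORR; for marrow CR it also reaches rw-ORR. DOR and rw-DOR are affected through who enters them. Marrow CR does not enter the primary CR rate.

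**Step 4. The plan's own precision figure.** Table 8-5 gives 11.6% to 18.9% for 15% at 400 patients. Clopper-Pearson with x = 60, n = 400:

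- lower = 2.5% quantile of Beta(60, 341) = 11.65%
- upper = 97.5% quantile of Beta(61, 340) = 18.88%
- half-width = (18.88 − 11.65) / 2 ≈ 3.6 points

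All 25 intervals of Table 8-5 reproduce, so the precision figures are not in dispute.

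**Step 5. Illustration of size.** Let q be the share of threshold-meeting CRs that do not last 4 weeks. The protocol gives no value; 5%, 10% and 20% are assumptions. The rate under Appendix 2 is observed rate × (1 − q), at n = 400 (exact 95% CI in brackets):

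| Observed | q = 5% | q = 10% | q = 20% |
|---|---|---|---|
| 10% | 9.5% (6.8–12.8) | 9.0% (6.4–12.2) | 8.0% (5.5–11.1) |
| 15% | 14.25% (11.0–18.1) | 13.5% (10.3–17.2) | 12.0% (9.0–15.6) |
| 20% | 19.0% (15.3–23.2) | 18.0% (14.4–22.1) | 16.0% (12.5–20.0) |

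**Step 6. What the assumed shares imply.** If CR duration were exponential (a further assumption) with median m months, the share ending within 28 days (28 / 30.4375 = 0.92 months) would be 1 − 2^(−0.92/m): 5% for m = 12, 10% for m = 6 and 19% for m = 3. The 20% end of the range therefore needs a median CR duration of about 3 months.

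**The case against.** The strongest reply is that Table 8-1 is silent on duration and does not waive it. It cites IWG 2006, Appendix 2 is part of the same protocol, and Section 8.10 says that all IWG response criteria will be ascertained. A hematologist adjudicates every CR and PR and could read the 4 weeks in. The same-sample footnote is a rule on co-timing and does not bar a look at later counts.

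This stands in part. A reader might infer that the primary CR rate is simply not the endpoint named in the objective; the documents do not support that, because the omission could be filled at adjudication. It does not remove the need to reconcile. The CR and PR rows import only the threshold, the marrow CR row cites nothing, and marrow CR is not among the responses sent for adjudication. No section says whether or how the 4 weeks are checked.

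Three other stronger readings also fail:

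- *The study will overstate CR.* This holds only relative to Appendix 2 applied in full. Section 8.10 warns that unavailable marrows lead to underestimated CR and PR, so the net direction is unknown.
- *A recorded duration of CR under 4 weeks proves a short response.* It does not. That duration starts at the first documentation of CR, and the marrow and blood may precede it by up to 4 weeks.
- *The comparison will be biased in a known direction.* The protocol does not say whether Study 5F9005 applied the 4 weeks. If it did and this study did not, the azacitidine rate would be raised and the apparent contribution of magrolimab reduced.

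**Conclusion.** The inconsistency is real and lies within the protocol: Table 8-1 states no persistence requirement for CR, PR or marrow CR, and Appendix 2 states 4 weeks for all three. Because this concerns the definition of the primary endpoint, it is more than a detail to be left for later.

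The direction relative to Appendix 2 is certain; the size is not. With 5% to 20% short-lived CRs, a 15% rate falls by 0.75 to 3 points. Over most of that range the shift is well inside the confidence interval, and only the top approaches its half-width. The shares are assumptions, and the point does not depend on them. It is worth correcting before the response algorithms are validated, but it does not show that the CR rate will be wrong.

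**What to change.** In the CR, PR and marrow CR rows of Table 8-1, state that the 4-week minimum of Appendix 2 applies and what chart evidence satisfies or fails it: later blood counts, transfusion records, and documented relapse or progression. No repeat marrow should be required, since Section 8.10 says these are not routine. The rule must also say how two cases are handled: counts that slip below the CR threshold without meeting a relapse criterion, and transient count drops on treatment. A check based on relapse and progression criteria alone would miss the first and might wrongly remove the second.

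Report CR with and without the persistence condition, and list separately the responses with no record in the following 28 days, so that sparse charts are neither credited nor penalised unseen. Apply the same rule on both sides of the comparison with Study 5F9005. If the sponsor decides not to apply the duration, the endpoint should be labelled as IWG 2006 thresholds without duration wherever it is reported.

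The cost is an edit to three table rows and a small programming check. Table 8-4 already collects blood counts at visits and after treatment, transfusions at visits, and progression dates. The CR rate may come out slightly lower.

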### 8.1.2. Secondary Endpoints

**Real -World Complete Remission (rw-CR) Rate** is defined as the proportion of patients who achieve a CR as documented within their EHRs with or without confirmation of corresponding BM and peripheral blood parameters as defined per IWG 2006 MDS response criteria, during the treatment period with AZA or prior to the initiation of next MDS treatment.

**Objective Response Rate (ORR)** is defined as the proportion of patients who achieve a CR, or PR as documented within their EHRs with confirmation of corresponding BM and peripheral blood parameters as defined per IWG 2006 MDS response criteria, or achieve an mCR or HI, during the treatment period with AZA or prior to the initiation of next MDS treatment.

**Real -World Objective Response Rate (rw-ORR)** is defined as the proportion of patients who achieve a CR, or PR, as documented within their EHRs with or without confirmation of corresponding BM and peripheral blood parameters as defined per IWG 2006 MDS response criteria, or achieve an mCR or HI, during the treatment period with AZA or prior to the initiation of next MDS treatment.

**Duration of CR (DCR)** is defined as the interval from the first EHR documentation of a CR with confirmation of corresponding BM and peripheral blood parameters as defined per IWG 2006 MDS response criteria to the earlier of the first documentation of relapse, disease progression, or death from any cause.

**rw-DCR** is defined as the interval from the first EHR documentation of a CR with or without confirmation of corresponding BM and peripheral blood parameters as defined per IWG 2006 MDS response criteria to the earlier of the first documentation of relapse, disease progression, or death from any cause.

**Duration of Response (DOR)** is defined as the interval from when the criteria are first met for OR to the earlier of the first documentation of relapse, disease progression, or death from any cause.

**rw-DOR** is defined as the interval from when the criteria for rw-OR are first met to the earlier of the first documentation of relapse, disease progression, or death from any cause.

**Progression -Free Survival** is defined as the interval from the date of initiation of AZA to the earlier date of the first documentation of relapse, disease progression or death from any cause.

**Time to the next treatment** is defined as the interval from the date of initiation of treatment with AZA to the earlier date of the initiation of next anti-leukemic treatment of MDS (excluding palliative care or palliative radiation) or death from any cause.

**Overall Survival** is defined as the interval from the date of initiation of AZA to death from any cause.

### 8.1.3. Exploratory Endpoints

CCI

[REDACTED]

[REDACTED]

[REDACTED]

[REDACTED]

### 8.1.4. Study approach

Two types of variables will be collected and analyzed in the study as categorized below:

- *Structured*: these are controlled, mapped fields of the EHR that can be extracted through queries of the iKM database
- *Unstructured*: this is information contained in unstructured fields of the EHR (eg, progress notes, scan reports) that is collected through chart review

In addition, supplemental vitality status information from the LADMF will be used.

The data collection during the study will be conducted using a staged approach.

**Stage 1:** The purpose of this stage is to assess patient attrition and completeness of data elements. The following steps will be included:

- Identify study population from structured data (by applying inclusion/exclusion criteria using structured data).
- Develop a pilot chart review tool focusing on study endpoints (electronic Case Report Form [eCRF]).
- Perform pilot chart review for about 20 patients randomly selected from the study population (first 20 qualified patients among a total of 40 patients selected using SAS® with a random seed).

- Provide a data summary assessing completeness of data elements focusing on variables related to endpoints (ie, response/progression) and important covariates.
- Data analysis will not be performed during Stage 1.

**Stage 2:** The purpose of this stage is to expand chart review to the full population. Depending on the data completeness assessment of Stage 1, the sponsor may proceed to Stage 2 of the chart review for the full population.

- Finalize the eCRF based on Stage 1 assessment.
- Modify protocol, if required, based on data availability and completeness.
- Perform chart reviews among the full sample that meet additional inclusion/exclusion criteria in charts.
- Perform data analysis for the whole population including those in Stage 1.

## **8.2. Setting**

Patients who fulfill the inclusion criteria will be identified from the iKM EHR database.

Patients who were initiated on AZA prior to 01 January 2020 will be eligible for enrolment into the study allowing a minimum of 1-year follow-up.

- In Stage 1, all patients who meet the inclusion/exclusion criteria based on structured data and who initiated AZA as first line treatment between 01 January 2014 through 01 January 2020 will be identified. About twenty patients will be randomly selected among the patients for a pilot chart review.
- In Stage 2, chart review will be performed in all patients who initiated AZA from 01 January 2014 to 01 January 2020.

The index date is defined as the initiation date of AZA monotherapy in the firstline setting for higher-risk MDS.

Patients' baseline information will be assessed based on data collected, defined as below:

- For peripheral blasts, Hb, platelets, neutrophils: the latest assessment within 30 days on or prior to the index date will be used as baseline value. If no assessment is available within 30 days on or prior to the index date, the earliest assessment within 7 days after the index date will be considered as baseline value.
- For age, weight, Eastern Cooperative Oncology Group (ECOG) score, BM blasts, all other labs (except Hb, platelets, and neutrophils): the latest assessment within 30 days on or prior to the index date will be used as baseline value. If no assessment is available within 30 days on or prior to the index date, the earliest assessment within 30 days after the index date will be considered as baseline value.

- For height, IPSS-R, cytogenetic risk, transfusion dependence: the latest assessment within 30 days prior to the MDS diagnosis date up to the index date will be used as baseline value.
- For MDS classification and secondary MDS: the latest assessment on or prior to the index date will be used as baseline value. If no assessment is available on or prior to the index date, the earliest assessment after the index date will be considered as baseline value.

Patients' prior supportive treatments before initiating AZA for higher-risk MDS will be assessed during patients' prior medical histories, defined as patients' available histories in the iKM EHR. This will vary based on the length of disease and the time within USON clinics. The prior medical history period will end the day prior to the index date.

Unstructured (chart review) patient level data, extracted from EHR through an eCRF, will be collected into an electronic data capture (EDC) system.

Structured patient level data will be directly extracted from the iKM EHR.

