| BM Blasts % at MDS Diagnosis  | 1&2   | Unstructured | X   |              |         |           |                       |
| BM Blasts % at AZA Initiation   | 1&2   | Unstructured | X   |              |         |           |                       |
| BM Blasts During Treatment  | 1&2   | Unstructured |   | X            | X       | X         | X                     |
| Peripheral Blasts During Treatment  | 1&2   | Unstructured |   | X            | X       | X         | X                     |

| Data to be Provided if Available or Applicable  | Stage | Source                    | Baseline (At AZA Initiation or Earlier as Applicable) | Study Period |         |           | Post-treatment Period |
|---|-------|---------------------------|---|--------------|---------|-----------|-----------------------|
|   |       |                           |   | Visit 1      | Visit 2 | Visit (n) | Post-treatment        |
| Requirement for Blood Transfusion (record units and frequency)  | 2     | Unstructured              | X   | X            | X       | X         |                       |
| ECOG/Karnofsky Performance Status/  | 1&2   | Structured                | X   | X            | X       | X         |                       |
| Comorbidity b  | 1&2   | Structured                | X   |              |         |           |                       |
| Prior Treatment for MDS Including Supportive Care c  | 1&2   | Structured + Unstructured | X   |              |         |           |                       |
| Information Collected at Baseline and During the Study   |       |                           |   |              |         |           |                       |
| Concomitant Medications   | 1&2   | Structured + Unstructured | X   | X            | X       | X         | X                     |
| Complete Blood Count d   | 1&2   | Structured                | X   | X            | X       | X         | X                     |
| Serum Chemistry e  | 1&2   | Structured f   | X   | X            | X       | X         | X                     |
| Liver Function Tests g   | 2     | Structured                | X   | X            | X       | X         | X                     |
| AZA Treatment-Related Data   |       |                           |   |              |         |           |                       |

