## 8.7. Data Analysis

Data analysis will be performed by Gilead Sciences. Internal independent biostatistician and/or epidemiologist will perform the propensity score model with access to the baseline data only. No outcome data will be provided to them.

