Death information is updated weekly in the LADMF and is as current as it is reported to the Social Security Administration. However, death dates recorded in the LADMF are not complete due to limitations on access to records for research purposes {Navar 2019}. LADMF and hospital death records were compared after access restrictions imposed in 2011 {Levin 2019}. After 2011, LADMF sensitivity for in-hospital deaths was 14.8% (compared with 88.9% before 2011) and 28.9% for out-of-hospital deaths (compared with 71.4% before 2011). The LADMF specificity, however, was greater than 99% both prior to and after 2011. Peters and colleagues (2017) compared capture of death dates in the LADMF with a multi-phased approach that assessed online databases (including LADMF), EHR records, and provider follow-up {Peterss 2017}. The authors reported that 42.7% of death records were identified by the LADMF, and the remainder were identified from another online database (32.6%), EHR records (22.2%), and provider follow-up (3.5%). Overall, the sensitivity was 58.5%, with 100% specificity.

In a study of the iKM EHR database and LADMF, it was observed that 93.3% of all death records were captured in structured fields and 6.7% of death records were solely identified by the LADMF. Among deaths recorded by both structured data and the LADMF, concordance was 88.0%. When both structured and unstructured data are available, 99.4% of death records are captured from these sources, with 0.6% of death records solely identified by the LADMF. Between 2015 and 2019, the proportion of death records captured by structured data trended upward (slope = 4.04).

Based on previous studies of other solid tumors, it is estimated that physician-assessed response will be available for greater than 60% of patients in the RWD. However, this may be impacted by BM reports and may vary considerably for patients with MDS. In standard clinical practice in the treatment of MDS, bone marrow biopsies are not routinely performed other than during diagnosis and at suspected disease progression. If BM biopsy results are unavailable for a significant proportion of patients, this will lead to an underestimate of the CR and PR rate (as defined in the Table 8-1) in the study. Therefore, the interpretation of data collected and analysed retrospectively will be dependent on the completeness and quality of the data.

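### Baseline marrow blasts may come from up to 30 days after azacitidine starts while older untreated marrows are barred, so mCR, PR and blast-based relapse can be misclassified in the patients who use this fallback

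*Protocol*

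**What the plan says.** Section 8.2 sets the index date at the first azacitidine dose and gives several baseline rules.

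- **BM blasts, ECOG, weight, most other labs** ("For age, weight, Eastern Cooperative Oncology Group (ECOG) score, BM blasts, all other labs (except Hb, platelets, and neutrophils"): first choice is "the latest assessment within 30 days on or prior to the index date will be used as baseline value". If there is none, "the earliest assessment within 30 days after the index date will be considered as baseline value".
- **Peripheral blasts, Hb, platelets, neutrophils**: same first choice, but the fallback is shorter: "the earliest assessment within 7 days after the index date will be considered as baseline value".
- **IPSS-R, cytogenetic risk, transfusion dependence, height**: latest value from 30 days before MDS diagnosis up to index, with no post-index fallback.
- **MDS classification and secondary MDS**: latest value on or before index. If there is none, "the earliest assessment after the index date will be considered as baseline value", with no time limit.

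Section 8.10 says that in practice "bone marrow biopsies are not routinely performed other than during diagnosis and at suspected disease progression". Table 8-4 lists "BM Blasts % at MDS Diagnosis" as its own item, separate from blasts at azacitidine initiation.

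Table 8-1 and Appendix 2 (Table 13-1) require a fall of at least 50% from pretreatment blasts for marrow CR (mCR) and PR, and count a return to the pretreatment percentage as relapse. Section 8.7 gives the propensity modellers baseline data only: "No outcome data will be provided to them".

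**The concern.** A value taken up to day +30 spans one monthly azacitidine cycle and is not untreated. Because marrows are routinely done only at diagnosis and at suspected progression, a patient who starts more than 30 days after the diagnostic marrow will foreseeably have either an on-treatment baseline or none, while an untreated value sits in the database.

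The rule is also out of line with its neighbours in section 8.2. IPSS-R may reach back to diagnosis and never looks past index. Peripheral counts may look only 7 days past it. BM blasts, the reference for response, get 30 days past index and no look-back to diagnosis.

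At stake are the secondary endpoints built on mCR, PR and relapse, and their use in the comparison with Study 5F9005 (section 8.7.4). There is a related risk for the propensity model: a value measured after treatment began can enter as baseline although the modellers are meant to see no outcome data.

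**Working it through.** **The plan's own figures.** The plan gives no number on this point. Its sizing figures, the exact intervals in Table 8-5, reproduce (100 of 400 gives 20.8% to 29.5%). They concern the CR rate and do not change here.

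**Which endpoints use a pretreatment blast value**

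- CR: absolute thresholds only (blasts at most 5%, Hb, platelets, neutrophils, no peripheral blasts). No pretreatment comparison, so the primary CR rate and rw-CR rate are unaffected.
- mCR: at most 5% and a fall of at least 50%. It needs no EHR documentation, is not listed for adjudication (section 8.9), and counts in ORR and rw-ORR (section 8.1.2).
- PR: a fall of at least 50% but still above 5%. It counts in ORR.
- Blast relapse: return to the pretreatment percentage. Relapse ends DCR, rw-DCR, DOR, rw-DOR and PFS.

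**Example (assumed values): 12% before treatment, 5% at day 28, 3% later**

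- Against 12%: (12 − 3)/12 = 75%, so mCR is met.
- Against 5%: (5 − 3)/5 = 40%, so mCR is not met.
- The blast-relapse threshold drops from 12% to 5%, a level that still satisfies the CR blast limit.

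**General form.** Let the true pretreatment value be B and the on-treatment reference B(1 − f). A fall of 50% from the reference is a true fall of 1 − 0.5(1 − f), and the relapse threshold is (1 − f) of the true value.

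| Assumed f | True fall needed | Relapse threshold, share of B |
|---|---|---|
| 0 | 50% | 100% |
| 0.1 | 55% | 90% |
| 0.2 | 60% | 80% |
| 0.3 | 65% | 70% |
| 0.5 | 75% | 50% |

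For mCR the 5% ceiling limits the effect. Half the reference is below 5% only when the reference is below 10%. With B = 15% and f = 0.3 the reference is 15 × 0.7 = 10.5% and the mCR ceiling stays at 5%, but the PR range narrows from above 5% up to 7.5% to above 5% up to 5.25%.

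**Opposite direction (assumed values): 8% before treatment, 12% on an early post-index marrow, 4.5% later**

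- Against 8%: (8 − 4.5)/8 = 43.8%, not met.
- Against 12%: (12 − 4.5)/12 = 62.5%, mCR met.
- The relapse threshold rises from 8% to 12%.

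**Illustrative size.** Assume a true combined PR/mCR rate of 20%, a share s of patients using the fallback, and a fraction q of their responses lost. The observed rate is 20 × (1 − s × q).

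- s = 0.05, q = 0.25: 20 × 0.9875 = 19.8%.
- s = 0.30, q = 1: 20 × 0.70 = 14.0%.

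The protocol gives none of the 20%, s, q or f.

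**The case against.** The strongest reply is that the link to response is not written down. Section 8.2 defines baseline, while Table 8-1 says pretreatment, which read literally excludes a day-28 marrow. The diagnostic value is abstracted and could serve. This stands as a limit on certainty but does not remove the problem: no other definition is given, section 8.8 has outcomes derived by algorithm to avoid manual interpretation, and the section 8.2 baseline is the natural input.

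Other points stand in part:

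- If marrows are mostly done at diagnosis and suspected progression, one in days +1 to +30 should be uncommon. That limits the number affected, and a marrow done for suspected progression can bias the other way.
- HI also counts toward ORR and rw-ORR, so a lost mCR need not be a lost responder. Relapse has non-blast criteria. PR and rw-PR are adjudicated, and rw-PR needs only EHR documentation.
- Windows may reasonably differ by variable. An old diagnostic marrow can be a poor reference if blasts changed before treatment, so recency against completeness is a real trade-off.
- The open-ended fallback for MDS classification should rarely apply, because Inclusion 2 requires a documented histological diagnosis.

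Some stronger readings are tempting but unsupported. A reader might infer that patients with no marrow from day −30 to +30 cannot be PR or mCR at all. Nothing says so, and the diagnostic marrow remains available. A reader might infer that a day-28 marrow used as baseline is disqualified as a response. No section states this. Nor do the documents show that the propensity covariates are wrong: the protocol lists none and leaves the comparison to an analysis plan that was not available here.

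**Conclusion.** The point holds in limited form. Section 8.2 fixes a rule that admits an on-treatment marrow as baseline blasts and bars an older untreated one already collected. If that baseline serves as the pretreatment reference, mCR, PR and blast-based relapse can be misclassified in patients with no marrow from day −30 to 0. Exposed are ORR, rw-ORR (through mCR), DCR, DOR, rw-DCR, rw-DOR and PFS. It would be wrong to read this as a threat to the primary result, since the CR rate uses absolute thresholds.

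The size cannot be fixed from the protocol. Direction varies by patient. If early blasts have fallen, responses are undercounted and relapse is called early, which makes azacitidine alone look worse against Study 5F9005. If they have risen, the bias reverses. For the propensity model this is a risk, not a demonstrated error: ECOG, BM blasts and most labs can carry post-index values, while IPSS-R, cytogenetic risk and transfusion dependence cannot.

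**What to change.** 1. Define pretreatment BM blasts for PR, mCR, relapse and PD as the latest marrow on or before the index date, looking back to 30 days before MDS diagnosis, as section 8.2 already does for IPSS-R. Never use a post-index marrow as the reference in the main analysis.
2. Report the number of patients by marrow source and by marrow age at index, with a sensitivity analysis limited to marrows within 30 days before index.
3. For any covariate entering the propensity model, use values on or before index in the main analysis and keep post-index fallback values for sensitivity analysis only.

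The cost is derivation wording. The diagnostic marrow is already abstracted, section 8.3 provides study days relative to index from which marrow age follows, and section 8.1.4 allows protocol changes after Stage 1. The downsides are some older marrow references, which the sensitivity analysis addresses, and a few more missing covariate values.
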